6.1 Study design

Single-blind randomized clinical trial.

6.2 Sample size

The sample size was calculated with a formula to compare two means:

$$n = \frac{K(\sigma_1^2 + \sigma_2^2)}{(\mu_1 - \mu_2)^2}$$

Figure 5. Applied formula to calculate the sample size.

Source: Taken from García in 2013(104).

The sample size was determined through a study that assessed the impact of physical training on metabolic alterations. The pre-intervention measurements were 131.31 ± 22.53 , and the post-intervention measurements were 116.90 ± 12.88 (65)

Error $\alpha = .05$

Error $\beta = 0.2$ (20%)

Power $1 - \beta = .8$ (80)

$K = 6.2$

$\sigma^2 = 22.53$

$\sigma^2 = 12.88$

$\mu_1 = 131.31$

$\mu_2 = 116.90$

$n = 20 \pm 20\%$.

$n = 24$ subjects per group

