2.4. Impact of physical exercise on metabolic disorders

Physical activity (PA) encompasses any bodily movement generated by skeletal muscles, requiring energy expenditure and is categorized into intensity levels: light, moderate, and vigorous(1). In 2022, the World Health Organization (WHO) recommends engaging in PA through planned, repetitive, and directed physical exercise. The goal is to improve and maintain physical fitness, involving body and muscle movement to enhance strength, speed, endurance, or flexibility, thereby promoting cardiovascular health(52). Likewise, PA aims to tailor exercise to individual needs, considering diverse physical capacities, since each person may have their advantages and limitations. Not least, PA aims to maintain proper warm-up, central exercise, and cool-down phases for effective and safe practice, ultimately promoting an active and healthy lifestyle(64).

Sequi in 2020 and Primo in 2022 reaffirmed the importance of physical exercise (PE) in individuals with morbidities related to cardiovascular diseases, as it brings considerable health benefits for those with these disorders(63,64). For instance, a study conducted by Chávez and colleagues in 2021 demonstrated that implementing an aerobic physical exercise program (such as walking, jogging, swimming, and dancing) for 20 to 30 minutes over 13 weeks among higher education students in Mexico could significantly reduce parameters associated with metabolic disorders. At the end of his intervention, he led to a considerable reduction of these parameters in this population. The results showed a decrease in abdominal circumference from $110.88\text{cm} \pm 14.27$ in the pretest to $106.90\text{cm} \pm 14.41$ in the posttest, as well

as a reduction in triglycerides from 131.31 mg/dl \pm 22.53 to 116.90 mg/dl \pm 12.88 and a reduction of the alteration in glucose, that went from 94.69 mg/dl \pm 7.98 to 92.50 mg/dl \pm 5.52. The author attributes these results largely to the adequate application of the Frequency, Intensity, Time, Type of activity, and Progression of load (FITT) principles, which are part of exercise prescription(65).

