5.3 Hypothesis

Hi. The implementation of an aerobic physical exercise program for eight weeks will have effects on at least one of the levels of metabolic disorders such as: the reduction of blood pressure, abdominal obesity, altered glucose levels, and increasing HDL in the study population

H0. The implementation of an aerobic physical exercise program for eight weeks will not have effects on any of the levels of metabolic disorders such as: the reduction of blood pressure, abdominal obesity, altered glucose levels, and increasing HDL in the study population

6. Methods and materials

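### The 80% power in section 6.2 is for triglycerides only; for waist and glucose, which the hypothesis lists, the same formula and source study give about 24% and 29% at 24 per group

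*Combined protocol and SAP*

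**What the plan says.** Section 6.2 uses the formula for comparing two means, n = K(σ1² + σ2²)/(μ1 − μ2)², with α = 0.05, power 0.80 and K = 6.2. It reaches 20 per group, then 24 after adding 20%. On the source of the inputs it says only "The sample size was determined through a study that assessed the impact of physical training on metabolic alterations". It then gives one pair of values: "The pre-intervention measurements were 131.31 ± 22.53 , and the post-intervention measurements were 116.90 ± 12.88 (65". The marker is not named.

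Section 2.4 describes the same source study (reference 65) and identifies the pair: "as a reduction in triglycerides from 131.31 mg/dl \pm 22.53 to 116.90 mg/dl \pm 12.88". The same paragraph reports abdominal circumference, 110.88 ± 14.27 to 106.90 ± 14.41 cm, and "a reduction of the alteration in glucose, that went from 94.69 mg/dl" ± 7.98 to 92.50 ± 5.52 mg/dl.

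Section 5.3 states that the programme "will have effects on at least one of the levels of metabolic disorders such as" blood pressure, abdominal obesity, glucose and HDL. Sections 5.1 and 5.2.1 list the same four. Triglycerides are in none of these three lists, although they appear in the abstract, in the specific objectives (5.2.2), in Table 5 and in section 11. No primary outcome is named.

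Section 11 compares the groups with independent-sample t-tests or Mann-Whitney tests and calls p ≤ 0.05 significant. It does not say whether tests are one- or two-sided.

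**The concern.** The plan contains one power figure. It belongs to a marker that section 6.2 does not name and that the hypothesis does not list. A reader who sees 80% in 6.2 next to the hypothesis in 5.3 would naturally apply it to the listed outcomes. For two of them, waist and glucose, the source study supplies what is needed to test that reading, and their standardised changes are much smaller than the triglyceride one.

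What is at stake is the interpretation of those two results. If power is in fact about one in four, a non-significant waist or glucose comparison is more likely than not even when effects of the source study's size are real. Set against an unqualified 80%, it could be reported as evidence that the programme does not affect that marker.

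**Working it through.** **Inputs.** The formula, K = 6.2, α, power and n = 24 come from section 6.2. The means and SDs come from section 2.4, all from the same source study. The between-group test comes from section 11.

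**Sidedness implied by K.** For 80% power, one-sided 5% gives (1.645 + 0.842)² = 6.18. Two-sided 5% gives 7.85. So K = 6.2 is a one-sided value.

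**The plan's own figure reproduces.** Triglycerides: 6.2 × (22.53² + 12.88²)/(131.31 − 116.90)² = 6.2 × 673.50/207.65 = 20.1, and 20 × 1.20 = 24.

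**Same formula, waist.** 6.2 × (14.27² + 14.41²)/(110.88 − 106.90)² = 6.2 × 411.28/15.84 = 161 per group.

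**Same formula, glucose.** 6.2 × (7.98² + 5.52²)/(94.69 − 92.50)² = 6.2 × 94.15/4.796 = 121.7, so 122 per group.

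With the two-sided constant 7.85, waist and glucose need 204 and 155 per group.

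**Power.** The common SD is the root mean square of the two SDs. The noncentrality is (difference/SD) × √(n/2), with 2n − 2 degrees of freedom (noncentral t).

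| Outcome | Difference/SD | One-sided, n = 24 | Two-sided, n = 24 | One-sided, n = 20 | Two-sided, n = 20 |
|---|---|---|---|---|---|
| Triglycerides | 14.41/18.35 = 0.79 | 85% | 76% | 79% | 68% |
| Waist | 3.98/14.34 = 0.28 | 24% | 16% | 22% | 14% |
| Glucose | 2.19/6.86 = 0.32 | 29% | 19% | 26% | 17% |

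The n = 20 columns show the position if only the pre-inflation number is evaluable in each group.

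**Effect of baseline adjustment.** Adjusting for baseline multiplies the SD by √(1 − ρ²), where ρ is the correlation between baseline and week 8. The documents give no value for ρ, so the following are assumptions. One-sided power at 24 per group is about 38% (waist) and 45% (glucose) at ρ = 0.7, and about 70% and 80% at ρ = 0.9. To reach about 80%, ρ must be √(1 − 24/161) = 0.92 for waist and √(1 − 24/121.7) = 0.90 for glucose.

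**Outcomes that cannot be checked.** The documents give no HDL figure from this source. Section 3 reports a change of 143.20 to 127.40 mmHg from the same study, but labels it heart rate and gives no SD.

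**The case against.** **Sizing a trial on one outcome is ordinary practice.** The calculation in 6.2 is right, its inputs can be traced to triglycerides, and nowhere does the plan claim 80% for every outcome. That stands. What remains is that 6.2 does not name its outcome, no primary outcome is named elsewhere, and the three statements of purpose leave triglycerides out. The hypothesis list is introduced as examples, so triglycerides could be read into it. The 80% would then still be for triglycerides alone.

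**A reader might infer that no listed outcome has adequate power.** The documents do not support that. If the mmHg pair in section 3 is blood pressure, as its unit suggests, 24 per group gives at least 80% one-sided power for any SD up to √(24 × 15.8²/(2 × 6.2)) = 22 mmHg. Section 2.8.3 has another mmHg pair, also labelled heart rate and from a different source (136 ± 5.9 to 124.5 ± 6.8), which would need about 4 per group. The labels are too ambiguous to show adequate power, but they rule out a claim about all four outcomes.

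**A reader might infer that the marker with the largest standardised change was picked.** This cannot be known. A change of 15.8 mmHg exceeds the triglyceride value of 0.785 SD for any SD below 15.8/0.785 = 20 mmHg.

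**A reader might infer that a null waist or glucose result would keep H0.** It would not. The hypothesis concerns at least one marker, so every marker would have to fail. Power per outcome is not the power of that hypothesis. For these two outcomes alone, assuming independence and no multiplicity control, power for at least one is 1 − (1 − 0.243)(1 − 0.289) = 46% one-sided.

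**The percentages are conditional on borrowed inputs.** The SDs come from a study whose title in the bibliography describes university academics with metabolic syndrome, while this trial enrols students aged 18 to 25. The SDs here may differ in either direction.

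**Conclusion.** The point holds for waist and glucose. The stated 80% is a one-sided figure for triglycerides. Under the plan's own formula, source study and K, waist needs 161 per group and glucose 122, so 24 per group gives about 24% and 29% one-sided, or 16% and 19% two-sided. Nothing can be concluded for HDL or blood pressure.

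These figures rest on the plan's convention: the pre and post SDs stand in for the two group SDs, and a one-group pre-post change stands in for the difference between arms. The control arm walks at 57% to 76% of maximum heart rate three times a week (section 9, Annexe 11). If walking also improves these markers, the true contrast is smaller and power is lower than shown. An analysis adjusted for baseline could raise it substantially, but only at high correlations, and section 11 does not clearly plan one: its multivariate analysis is not defined.

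**What to change.** **Section 6.2.**
- Name triglycerides as the outcome behind the calculation, and state that the 80% applies to it alone and is one-sided, as K = 6.2 implies. If testing is to be two-sided, give the corresponding triglyceride power: about 76% at 24 per group and 68% with 20 evaluable.
- Add one line with the waist and glucose power at 24 per group for the planned independent t-test: 24% and 29% one-sided, 16% and 19% two-sided.
- Add the correlation-based range only if section 11 is also changed to specify a baseline-adjusted comparison. Otherwise it would describe an analysis that is not planned.

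**Section 11.**
- State whether tests are one- or two-sided.
- State that the arm difference with its 95% CI will be reported for waist and glucose, and that p > 0.05 on either will not be read as absence of effect.

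The cost is a short paragraph in 6.2 and one or two sentences in section 11. No extra participants or measurements are needed.

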This study is a simple randomized clinical trial, its **objective** is to evaluate the effect of an aerobic physical exercise program on the reduction of triglycerides, blood pressure, abdominal obesity, altered glucose levels, and the increase in HDL in college-level students at the University of Colima, due to the high prevalence of obesity, a sedentary lifestyle, and physical inactivity in Mexican population, all of which contribute to a high risk for the development of metabolic disorders and cardiovascular diseases. **Methods and Materials:** A simple randomized clinical trial will be conducted with a **sample** of 48 voluntary students from the University of Colima, divided into two groups of 24 people. **Instruments:** IPA-Q questionnaire (*Annex 6*), waist circumference (*Annex 7*), blood pressure (*Annex 8*), blood extraction by a venous puncture for HDL, triglycerides, and blood glucose (*Annex 9*), Queen's College Step Test (*Annex 10*). **Procedure:** Once all the information from the tests is collected and processed, inclusion criteria (*table 2*) will be taken into consideration to obtain the total sample. Simple randomization will be carried out through a bag of sealed envelopes that will contain the letter of the group to which the subject belongs. Each participant will draw an envelope, write their name on it and hand it to the supervisor. Afterwards, these envelopes will be opened and participants will be assigned to the groups following the simple blind criteria, according to the letter on the envelope. The Experimental Group will undergo an aerobic physical exercise (APE) program involving jogging, swimming, and static cycling, three times a week with a duration of 60 minutes per exercise session with a progressive intensity, which will start at 57%-63% of the maximum heart rate (HRmax) in the first 4 weeks of the study, and will increase to 64% -76% in the final four weeks, fulfilling the principle of progressive overload. The control group will perform aerobic physical exercise, which will be walking at 57% to 76% of HRmax. **Expected results:** This intervention will lead to favourable changes in the disorders experienced by the intervention population and, at the same time, confirm the effectiveness of the planned aerobic physical exercise in reducing these risks.

Keywords: Exercise, Obesity, HDL, Triglycerides, Hypertension.

1. Introduction

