The importance of moderate and vigorous aerobic physical exercise could reduce the risk of cardiovascular and cerebrovascular diseases in individuals with metabolic alterations(94,95).

Jaramillo in 2019, Sequi in 2020, and Primo in 2022 determined that MVPA can decrease various metabolic disorders (such as triglycerides, hypertension, abdominal obesity, and hyperglycemia) by 3% to 10% over 10 weeks (63,64,85). Along the same lines, Chávez in 2021 implemented an aerobic exercise program to assess its effect on reducing metabolic disorders in university students over thirteen weeks. The program involved four weekly sessions, each lasting 20 to 30 minutes. The results showed changes in triglycerides (131.31 mg/dl, post 116.90 mg/dl), heart rate (143.20 mmHg, post 127.40 mmHg) and abdominal obesity (110.88 cm, post 106.90 cm) (65).

Considering the execution timeline and findings from Chávez's study and other mentioned research, this study proposes an improvement: reducing the intervention duration from 13 to 8 weeks and decreasing the intervention frequency from 4 to 3 days. Considering that the volume of work will increase from 30 minutes to 60 minutes per session, complemented by personalized physical exercise planning for each subject. The objective of this modification is to achieve the same beneficial changes in metabolic alterations while reducing the intervention time.

Laboratory tests and anthropometric measurements in each patient are part of the assessment protocol at both the primary and secondary levels of care for screening non-communicable diseases, which is reflected in the feasibility of the study. It should be noted that the laboratory reagents available are easy to use and essential for comprehensive diagnosis, complying with the operational definitions of each of the suspected diseases, taking into account the clinical practice guide or international guides such as ADA or ATP III. Additionally, the research team possesses the experience and infrastructure necessary for screening and monitoring subjects participating in the study (39, 95)

The vulnerability of the study lies in patient recruitment, as it involves a young population that may not recognize risk factors for non-communicable diseases, and those who participate, often lack adherence to interventions due to various factors such as time constraints related to work, school activities, and extracurricular commitments.

4. Problem statement

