6.3. Selection criteria

Table 4. Selection criteria

Inclusion	Exclusion	Elimination
University of Colima students linked to the central campus.	Motor limitations that may hinder the performance of physical exercise.	Musculoskeletal injuries during the study period.
Students aged between 18		Unforeseen Medical Events: Unexpected medical

and 25 years old.	Pregnancy or lactation.	situations that could influence study results, such as hospitalizations, serious illnesses, or surgeries.
Authorization to participate in the project with a signed informed consent.	High Vigorous Physical Activity Level according to the IPA-Q.	Non-Compliance with Follow-Up: Subjects failing to meet a minimum of 80% (19 out of 24 sessions) of the stipulated physical conditioning program time.
Suffer from at least one of the parameters of metabolic disorders or cardiovascular risk (Hyperglycemia, decreased DHL, elevated triglycerides, abdominal obesity or hypertension) following the clinical assessment (Considering the criteria established by the ADA and ATPIII).	To be currently under pharmacological treatment to manage altered metabolic levels.	Initiation of clinical treatment that may affect protocol results, such as medications that reduce alterations.
		Participants who voluntarily withdraw from the study.

Source: self-made.

7. Variable operationalisation.

Table 5. Dependent variables.

Dependent variables	Operational definition	Nature	Scale	Instrument
Glucose Alterations	Fasting plasmatic glucose concentration determination:	Quantitative Continuous Ratio	It is considered an alteration >110 mg/dl	Fasting serum glucose

Abdominal Circumference	Total abdominal perimeter Abdominal obesity based on abdominal circumference.	Quantitative Continuous Ratio	It is considered an alteration when: Males >90cm Females >85 cm	Circumferential measurement with ISAK tape measure
HDL (High-Density Lipoprotein)	Serum concentration of high-density lipoprotein in milligrams per deciliter (mg/dl)	Quantitative Continuous Ratio	It is considered an alteration when: Males < 40 mg/dl, Females < 50 mg/dl	Lipid profile test
Triglycerides	Serum concentration of triglycerides in milligrams per deciliter (mg/dl)	Quantitative Continuous Ratio	It is considered an alteration when: Males >150 mg/dl Females >150 mg/dl	Lipid profile test

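### Section 6.2 adds 20% to a rounded-down 20; if the 20% is meant as cover for losses, 24 per group covers 3 or 4 losses (12.5% or 16.7%), not 20%

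*Combined protocol and SAP*

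**What the plan says.** Section 6.2 uses a formula for comparing two means, n = K(σ₁² + σ₂²)/(μ₁ − μ₂)², with alpha 0.05, power 80% and K = 6.2. The inputs are triglyceride values from one cited exercise study: means 131.31 and 116.90, SDs 22.53 and 12.88. It then gives n as 20 with a plus-or-minus sign and 20%, and ends at "n = 24$ subjects per group". The abstract repeats the result: 48 students, "divided into two groups of 24 people".

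Section 6.2 attaches no purpose to the 20%. Two other places bear on it:

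- Section 3 (Justification) names recruitment and adherence as the study's weak point and says that participants "often lack adherence to interventions due to various factors such as time constraints".
- Section 6.3, Table 4, lists five grounds for elimination: injury, unexpected medical events, poor attendance, start of a treatment that could affect results, and withdrawal. Two of these read "Subjects failing to meet a minimum of 80% (19 out of 24 sessions" and "Participants who voluntarily withdraw from the study".

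Section 11 does not say whether eliminated participants are analysed, or how missing values are handled.

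**The concern.** There are two separate steps to question. First, a calculated minimum of 20.11 is carried forward as 20, although a minimum number of participants is rounded up. Second, the 20% is added by multiplying by 1.2. That is not the inverse of losing 20%: to have n left after losing a fraction d, one must enrol n/(1 − d).

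What is at stake is the margin for attrition. The 20% is the only allowance in the sample-size section. If the team tracks losses in the belief that it has 20% in hand, it will pass below its own required number sooner than expected.

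**Working it through.** **Inputs (section 6.2).** SDs 22.53 and 12.88; means 131.31 and 116.90; K = 6.2; 20% allowance; 24 per group. The two SDs are labelled as variances, but n = 20 is reached only if they are squared (unsquared, the formula gives 1.06). This is a labelling slip with no effect on n.

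**Reproducing the plan's figure.**

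- Difference: 131.31 − 116.90 = 14.41, and 14.41² = 207.648.
- Sum of variances: 22.53² + 12.88² = 673.495.
- n = 6.2 × 673.495 / 207.648 = 20.11. The plan writes 20; rounded up it is 21.
- 20 × 1.2 = 24, the plan's final number.

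**What K implies.** (1.645 + 0.842)² = 6.18, so K = 6.2 is the multiplier for a one-sided 0.05 test with 80% power. The two-sided value is (1.960 + 0.842)² = 7.85.

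**Taking 20% away again.** 24 × 0.8 = 19.2, that is 19 whole participants. This is below 21, below 20.11 and below the plan's 20, so the result does not depend on the rounding point.

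**Dividing instead of multiplying.**

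| Starting n | n / 0.8 | Per group |
|---|---|---|
| 20 (plan's rounding) | 25.00 | 25 |
| 20.11 (unrounded) | 25.14 | 26 |
| 21 (rounded up) | 26.25 | 27 |

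**Losses that 24 per group can absorb.** 24 − 21 = 3, and 3/24 = 12.5%. Against the plan's 20: 24 − 20 = 4, and 4/24 = 16.7%.

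**Power on the plan's own basis.** One-sided 0.05, normal approximation: power = Φ(14.41/√(673.495/n) − 1.645). For n = 19, 14.41/√35.447 = 2.42 and the power is Φ(0.775) = 78.1%.

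| n per group | One-sided power (normal) | One-sided power (t) |
|---|---|---|
| 24 | 85.9% | 85.0% |
| 21 | 81.6% | 80.4% |
| 20 | 79.9% | 78.6% |
| 19 | 78.1% | 76.7% |

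**The case against.** The strongest reply is that the plan never promises cover for a 20% loss. A reader might infer that section 6.2 states such a property and breaks it, but no passage calls the 20% dropout or says that the required number will remain after it. This stands: loss cover is an inference, although a well-supported one. The 20% is applied after the power calculation is complete, sections 3 and 6.3 both anticipate losses, and the documents offer no other purpose. The plus-or-minus sign does not help. Read literally it gives 16 to 24, with no reason for taking the upper end. It may also be a plus sign that was misread from the PDF, and nothing here rests on it.

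The second reply is that the effect is small, which also stands. With 20 left, power is 79.9%, so rounding to 20 costs about a tenth of a point against the 80% target. Part of the excess over 20 comes from rounding K up: with unrounded K the formula gives 20.05. Five losses out of 24 is 20.8%, slightly more than 20%; at exactly 19.2 per group power is 78.5%.

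A reader might also infer that the error leaves the trial with 68% power (65% by t), the two-sided figures at 19 per group. The documents do not support blaming that on the allowance. At 19 per group, moving from a one-sided to a two-sided test takes power from 78.1% to 67.7%, about 10 points, while the allowance accounts for about 2 (80% to 78.1%). Even with no losses, 24 per group gives 77.6% two-sided. That gap belongs to the choice of K, and section 11 does not state sidedness.

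Finally, the inputs are before-and-after values from one study used as if they were two groups, whereas this trial's control group also exercises. That is a larger uncertainty than 1 to 3 participants per group, but it does not alter the arithmetic.

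**Conclusion.** The point holds in a limited form. The formula's 20.11 should be carried as 21, and 24 per group does not cover a 20% loss by any rounding. The shortfall is 1 to 3 per group (25 to 27 against 24). The real margin is 3 or 4 losses per group, depending on whether 21 or 20 is taken as the requirement. On the plan's one-sided basis the cost at 19 per group is about 2 points of power.

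This rests on three assumptions: that the 20% is meant for losses, that eliminated participants drop out of the comparison, and that K = 6.2 and the other inputs are left as they are. If the 20% has another purpose, the criticism of the division falls away, but the line would still need an explanation. This is a correction to the sample-size statement, and it does not show that the trial must enrol more people.

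**What to change.** In section 6.2, say what the 20% is for and replace the line that carries it with wording such as:

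> The formula gives 20.1, rounded up to 21 per group. Enrolling 24 per group allows for 3 losses per group (12.5%), or 4 (16.7%) at 79.9% power. With 19 per group remaining, power is about 78%. These power figures are for the one-sided 0.05 test implied by K = 6.2.

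The cost is a few lines of text and a less favourable stated margin. Enrolment, procedures and the 48 in the abstract stay as they are. If the sponsor prefers to keep genuine cover for a 20% loss, the number is 25 to 27 per group (50 to 54 in total against 48), according to the rounding chosen.

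The sidedness of K should be settled as its own point. If K changes, the required n, the tolerated losses and the power figures in this wording must all be recalculated.
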